5.5 Subject Withdrawal

Subjects may voluntarily withdraw their consent from the study.

5.5.1 Reasons for Withdrawal

Subjects are free to withdraw from participation in the study at any time upon request.

5.5.2 Handling of Subject Withdrawals or Subject Discontinuation of Study Intervention

If a participant requests to be withdrawn from the study, the following must happen for official withdrawal:

- Principal Investigator (PI) calls and/or emails to explain instructions for withdrawal
- Mail/email them a copy of their signed consent along with letter from the PI and stamped envelope addressed to UIC/IHRP that includes instructions on how to withdraw
 - o If no response in 2 weeks, repeat mailing
- Instructions
 - Participant caregiver to write "I am withdrawing from this study" somewhere on the consent form and send it back in the envelope provided.
- If no response or returned consent form, participant remains in study. Continue to repeat procedure if participant continues to request withdrawal.
- Once a participant is withdrawn, a note should be placed in their clinic/WIC records stating this.

Families that withdraw will not be replaced.

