15.3 Informed Consent Process

Informed consent is a process that is initiated prior to the individual agreeing to participate in the study and continues throughout study participation. Extensive discussion of risks and possible benefits of study participation will be provided to participants and their families, if applicable. The RA will obtain written informed consent and parental permission from the caregiver before the start of the data collection. If the caregiver participant is not the legal guardian of the child but is the primary caregiver agreeing to participate, separate consent forms will completed by the caregiver participant and legal guardian. (An example of this is that sometimes grandmothers do the majority of the day-to-day care of a child but the mother is the legal guardian. In this instance, we would ask the mother to sign the parental permission informed consent for the child and the grandmother to sign the informed consent for herself.) A consent form describing in detail the study procedures and risks will be given to the participant. Consent forms will be IRB-approved, and the participant is required to read and review the document or have the document read to him or her. The RA will explain the research study to the participant and answer any questions that may arise. The participant will sign the informed consent document prior to conducting any studyrelated assessments or procedures. Participants will be given the opportunity to discuss the study with their surrogates or think about it prior to agreeing to participate. They may withdraw consent at any time throughout the course of the study. A copy of the informed consent document will be given to participants for their records. The rights and welfare of the participants will be protected by emphasizing to them that the quality of their clinical care will not be adversely affected if they decline to participate in this study.

The consent process will be documented in the clinical or research record.

All research staff, investigators, and clinical staff with access to data will undergo HIPAA and human subjects research training. Training is provided at the University of Illinois at Chicago through the Citi Program (*www.citiprogram.org*).

Consents for screening will be verbal, and written consent documents will be provided and signed when participants are enrolled in the trial. Note that assent is not used because all children will be under the age of 3 years old.

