APPENDIX D: CONTACT ATTEMPT AND WINDOW PROTOCOL

CO-OP Chicago

CONTACT ATTEMPT AND WINDOW PROTOCOL

Research Specialist: Data Collection

Windows

Type of Visit	Earliest start	Latest acceptable	
Baseline	NA	NA	
6-month	14 days before	60 days after	
12-month	Date due	90 days after	

Clock starts when randomized.

12-month due date does not change regardless of when 6-month data collection visit completed.

Attempts

- For main outcomes visit: 12-month
 - These are primary outcomes, need to try to get at all costs.
 - Contact every 2-4 days at varying times of day and varying types of mediums for first 2 weeks. Consider then reducing frequency of attempts but do not give up until window closed.
 - If phone not working, or no answer after 5 attempts, stop by home up to 2 times. If can talk with family, great. If not, then drop off letter.
 - If cannot drop off letter or no response to dropped off letter after 1 week, send certified letter.
 - o If no response to anything, at minimum try to call once a week until window closed.
 - o If ultimately family cannot do in person, do via telephone if feasible for family.
 - If phone not working/no answer, attempt to verify address and phone number at the subject's clinic/WIC.
 - If no answer from all phone numbers and letters, attempt to see if any scheduled appointments at subject's clinic/WIC. If yes, try to be at that appointment to talk with family before/after.
 - Track for each attempt
 - Date
 - Day of week
 - Time of day
 - Medium (phone call, text, email, letter, stopped at home) and number/address used
 - Comment section (note if family answered but can't talk now, family stood you up, talked with other family member and told to call back, etc)
- For 6-month
 - Same as 12-month but shorter window.

CHWs

Windows

4 visits over 12 months, preferred in person at home or other location face-to-face. Goal is 2 visits in first 6 months, 2 visits in second 6 months. Follow-up phone calls should be conducted after visits (total of 4).

- Additional contacts acceptable but not encouraged.
- CHW can call family to schedule as soon as randomization completed.
- Goal is one visit every 2-3 months
- No more than 2 in-person visits before the six month mark; no more than 2 in-person visits after the six month mark
- In-person visits cannot be closer than 30 days.

Attempts

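### A withdrawal request is said to be enough, yet it has no effect until an annotated consent copy comes back, and the status of contact and data in between is undefined

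*Combined protocol and SAP*

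**What the plan says.** Section 5.5.1 states the right without conditions: "Subjects are free to withdraw from participation in the study at any time upon request". Section 15.3 adds "They may withdraw consent at any time throughout the course of the study".

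Section 5.5.2 then sets out what a request leads to: "If a participant requests to be withdrawn from the study, the following must happen for official withdrawal". The PI contacts the family to explain the steps. A copy of the signed consent goes out by mail or email with a letter and a stamped envelope. The caregiver is to write a short withdrawal statement "somewhere on the consent form and send it back in the envelope provided". On silence the rule is "If no response in 2 weeks, repeat mailing", and after that "If no response or returned consent form, participant remains in study". For a family that asks again: "Continue to repeat procedure if participant continues to request withdrawal".

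Section 7.9 ends data collection for a subject who withdraws or is administratively withdrawn. The footnote to Appendix A ends both data collection and intervention for the same group. Neither mentions a family whose request is pending.

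Appendix D governs attempts to reach families. For the 12-month data collection it sets contact every 2 to 4 days for the first 2 weeks of attempts, then says "Consider then reducing frequency of attempts but do not give up until window closed". It allows for home stops and a certified letter if earlier attempts fail. A separate part covers attempts by the community health workers (CHWs). Neither part mentions a family that has asked to leave.

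**The concern.** Section 5.5.1 makes the request sufficient, while Section 5.5.2 gives it no effect, however often it is repeated, until a piece of paper is returned. Asking for written confirmation while honouring the request would be ordinary record-keeping. Here the default runs the other way: silence means continued participation, with no limit of time.

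Two things are at stake. The first is participant protection. A family that has said it wants to leave could still be approached for study visits. Section 8.1 reports limited reading ability among many adults in similar populations and in the pilot, yet leaving requires a handwritten statement and its return, with no oral alternative given.

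The second is the data. Section 12.3 plans an intention-to-treat analysis in which all randomized respondents are represented, missing outcomes are imputed, data are expected to be missing at random, and departures from that are watched for. The recorded reason for missingness is part of the evidence for that judgement. A family that asked to leave and never returned the form has no route to being recorded as withdrawn, so a deliberate departure could look like failure to locate. Reasons for leaving might also differ by arm, because only one arm has CHW contact during follow-up. The documents do not say whether data obtained after a request may be used.

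**Working it through.** No sample size, power or error-rate calculation is involved. The check is to follow one request through the sections in order.

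1. **The request is made.** Under 5.5.1 the subject is free to go. Under 5.5.2 a procedure begins and the subject is not yet officially withdrawn.
2. **The annotated copy is returned.** Both sections now agree that the subject is withdrawn, and 7.9 and Appendix A stop data collection. The only open question is the status of the days between request and return.
3. **Nothing is returned.** After 2 weeks the mailing is repeated. If there is still no return, 5.5.2 keeps the family in the study. Under 5.5.1 the family left at step 1. The two sections give opposite answers for the same family.
4. **The family asks again.** Section 5.5.2 repeats the same procedure, so step 3 can recur. No maximum number of rounds and no closing date are given.
5. **Contact and data while steps 3 and 4 run.** The stop in 7.9 and Appendix A is tied to withdrawal, which under 5.5.2 has not happened. Appendix D applies to participants and has no exception for a pending request. Nothing in the reviewed text suspends contact or data collection.
6. **How the family is recorded.** If no 12-month data are obtained and no form is returned, the family is not officially withdrawn. The natural entry is loss to follow-up. No field for the date of the request is described.

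The documents' own intervals give a sense of scale. If a 2-week wait for the form fell wholly within the first 2 weeks of contact attempts, one attempt every 2 to 4 days would give 14/4 = 3.5 to 14/2 = 7, or about 4 to 7 attempts. This shows only what the text permits; it does not estimate what would happen.

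The number of families affected cannot be calculated. Section 12.2 assumes 15% attrition at each follow-up but does not separate withdrawal from other loss, and no expected number of requests is given.

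**The case against.** The strongest reply is that a right and its documentation can coexist: 5.5.1 states the right, and 5.5.2 describes how it is made official. The procedure opens with the PI explaining the steps, the copy may be emailed, and the envelope is stamped. Outcome data also need the caregiver's active cooperation in scheduling, answering questions and presenting the child for photographs, so a family that refuses gives no data. And the consent form (Appendix J) and the Manual of Procedures, which were not available for review, might contain an interim rule.

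Much of this stands, and it rules out several stronger readings that a reader might infer.

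- A minimum delay of 2 weeks per request: not supported. Two weeks is only the trigger for a second mailing, and a prompt return could be quicker.
- A new signed form: not required. What is returned is a copy of the consent already signed, with a handwritten statement.
- Section 15.3 also making the request sufficient: not stated. It fixes when consent may be withdrawn, not how. Only 5.5.1 refers to a request.
- The protocol directing staff to pursue families who have asked to leave: not stated. Continued contact is inferred from the default in 5.5.2 and the lack of a hold. Appendix D also limits home stops to two and makes them follow failed phone contact.
- A count of affected dyads, reached by applying a guessed rate to the 420: no rate in the documents supports one.

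The default itself does not survive the reply. A rule that documents a request would still honour it when the paperwork fails; this one reverses it. An interim rule elsewhere could settle contact and data handling, but 5.5.1 and 5.5.2 would still disagree about a family that never returns the form.

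**Conclusion.** The contradiction between 5.5.1 and 5.5.2 is real and lies in the current text. It concerns the outcome when nothing is returned and the undefined period between request and confirmation. Continued research contact, continued data collection and misclassification as loss to follow-up are possible consequences of the wording, not instructions in it.

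The size is unknown. The documents neither show that the primary comparison would be affected nor allow that to be excluded. The case for correction rests on participant protection and on clean coding of missingness, and needs no assumed withdrawal rate. The conclusion about the interim period assumes that no rule in the consent form or Manual of Procedures fills the gap; the conflict between the two sections does not depend on that assumption.

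**What to change.** Reconcile 5.5.1, 5.5.2, 7.9, 15.3, Appendix A and Appendix D so that:

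- one rule states when a withdrawal request takes effect, and failure to return the form no longer overrides the request;
- written confirmation is kept as documentation of the request;
- the text says what happens to research contact and data collection between a request and its confirmation;
- the date of the first request is recorded in REDCap, and data collected after that date are flagged;
- Section 12.3 states whether flagged data enter the intention-to-treat analysis and how the reason for missingness is coded.

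Appendix D also governs CHW contact, so a blanket pause of that appendix would reach the intervention as well. How CHW contact is handled after a request is for the sponsor to settle when reconciling the sections; no rule for it is proposed here. The consent form and Manual of Procedures should be checked for consistency at the same time.

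The cost is protocol wording, one date field with its flag, and possibly a slightly higher recorded withdrawal count.

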5.6 Premature Termination or Suspension of Study

This study may be suspended or prematurely terminated if there is sufficient reasonable cause. Written notification, documenting the reason for study suspension or termination, will be provided by the suspending or terminating party to [name], funding agency, and regulatory authorities. If the study is prematurely terminated or suspended, the PI will promptly inform the IRB and will provide the reason(s) for the termination or suspension.

Circumstances that may warrant termination include, but are not limited to:

- Determination of unexpected, significant, or unacceptable risk to subjects.
- Insufficient adherence to protocol requirements.
- Data that are not sufficiently complete and/or evaluable.
- Determination of futility.

STUDY INTERVENTION 6

6.1 Study Behavioral or Social Intervention(s) Description

This study will test an oral health CHW intervention.

6.1.1. CHW Intervention Pedagogy

CHWs use social cognitive theory to help families shape and maintain behaviors.³⁸ The CO-OP Chicago Oral Health CHW intervention will apply formal self-management skills (problem solving, decision making, resource utilization, patient/doctor partnership, and taking action),³⁹⁻⁴⁴² in addition to the oral health core curriculum. CHWs will use Action Plans as a tool to teach these skills and take action. Action Plans are small goals for a specific change over a designated time period (Appendix E). The CHWs will start by providing education from the oral health core curriculum, but when they note a barrier in the delivery of the education, they will incorporate a relevant self-management skill and create an action. For example, a CHW may suspect the family is not brushing the child's teeth regularly but instead of just saying that, the CHW will have the family track how often the child is brushing over a one week period. The family will "self-discover" they do not brush as often as recommended. Then the CHW will have the family brainstorm as to why that might be (bathroom organization, parent work schedules, behavioral issues, etc.). Once they have a list of the problems, the family will create an Action Plan for one problem they want to work on. On subsequent CHW visits and follow-up telephone calls, CHWs revisit past Action Plans, revise them, and make new ones.

6.1.2. CHW Core Curriculum

1. Oral health basics	4. Weaning
a. What is caries	a. When to transition from bottle
b. Causes of caries	b. Sippy cup recommendations
c. Importance of caries prevention	n c. Nighttime feeding
2. Tooth brushing	5. Nutrition
a. When to start	a. Sugar-sweetened beverages
b. Frequency	b. Juice
c. Technique	c. Healthy foods
d. Equipment	6. Seeing the dentist
e. Toothpaste	a. When to start
3. Fluoride	b. What to expect

- a. Water
- b. Other sources

- - c. Frequency
- d. Role of the pediatrician

6.2 Administration of Intervention

Families will be offered 4 in-person visits and 4 phone call follow-ups over 12 months. The expectation is that two visits will occur in the first six months and two visits will occur in the second six months. The expectation for phone call follow-ups is that they will occur after the in-person visits, on a schedule that is determined by the family and CHW. Visits can occur at any location of the family's choosing. This could be the home, clinic, WIC, or other location.

At in-person visits, CHWs will spend 1-2 hours with the family. The first 15 minutes are spent in social engagement (getting to know the people in the family and the family's interests, as well as the family getting to know the CHW, or catching up socially if families are already known). CHWs will try to engage all family members in the visits if possible. At the first visit, the CHW will then administer the Caries-risk Assessment Tool⁴³ (Appendix F) for all family members present. CHWs will follow this with tailored education based upon the risk assessment results using a variety of live demonstration, pictorial, video, and written resources. The oral health topics are drawn from the Core Curriculum (Section 6.1.2, Appendix G). CHWs will generally apply popular education methods⁴⁴, meaning they will rarely use written materials. Instead they will engage the family in discussion using questions, stories, videos, and demonstrations. These are the same techniques and methods used in the CHW training. For equipment, CHWs will have computers with Wi-Fi access (via hotspots) to view videos. CHWs will have models for demonstrating tooth brushing and they will practice with families. CHWs will also facilitate family-wide dental care access by identifying accepting providers, providing families with provider contact information, and assisting to make appointments as needed. CHWs will have access to Purple Binder which is an online community resources search service (www.purplebinder.com). For the last 15 minutes of the visit, families will make Action Plans (Appendix E). At the start of all subsequent visits, Action Plans from the previous visit will be reviewed and discussed. CHWs will aim to address all the core curriculum topics over the one year intervention. After each visit, CHWs will call or text the caregiver during the subsequent month to follow-up on actions and reinforce concepts from the previous visit. The detailed core curriculum protocol and materials are included in Appendix G. CHWs will document topics covered and materials used immediately after each visit. (Form in Appendix H). Follow-up telephone calls will be conducted to review information and plans, address questions, and provide social support. (Appendix G)

6.3 Procedures for Training Interventionists and Monitoring Intervention Fidelity

6.3.1. CHW Training and Hiring

Because limited formal certification or licensing programs for CHWs exist nationally or locally,⁴⁵ training curriculums are developed for individual programs and are not standardized for any disease area. CHWs require training in disease-specific content,

building relationships, self-advocacy, teamwork and conflict resolution, crisis and emergency management, and home visitation before going into the field.^{13,45}

Phase I: Pre-Hire Training

Potential candidates for the CHW positions will be recruited through existing UIC programs, participating medical clinics and WIC sites, community list-serves, and word of mouth. Preference will be given to candidates who have already worked as CHWs and who have experience with the participating clinics or WIC centers. We plan to hold one training session on the west side and another on the south side of Chicago. Notices for the training will be distributed through the partner sites, UIC, and local CHW listserves. A cohort of 12-15 candidates will be selected from those who express interest to attend each pre-hire training. Pre-hire training serves several purposes: 1) The training builds community capacity and skills around oral health, 2) It allows investigators to determine the best candidates for the position, and 3) It provides a pool of back-up candidates for the future. In the pilot phase of this project, the CO-OP Chicago team built and tested a comprehensive oral health CHW training curriculum.²⁸ The manual is available at website (http://go.uic.edu/COOPChicago) and in the Manual of Procedures. This 4.5 hour training will be conducted by [name] and either [name] or the hygienist in English. The training concludes with standardized role plays to evaluate skills attainment and content delivery. Once both trainings are completed, the CHW positions will be posted, and trainees will be invited to apply. The training role play scores and observations will be compared. The best candidates will be interviewed and hired. Additional pre-hire trainings will be conducted if needed until the CHWs are hired.

Phase 2: Post-Hire Training

Three to four CHWs (3.0 FTE) will be hired. Once hired, CHWs will undergo additional training. If the CHWs have not previously worked or been trained as CHWs, they will undergo the UIC Coordinated Healthcare for Complex Kids (CHECK, *https://www.mycheck.uic.edu/* basic CHW training which was designed by [name] and is supervised currently by [name]:

Topics	Duration	
CHECK Overview: Medicare and Medicaid overview, CMS innovations awards, Inappropriate healthcare use, Goals and activities of CHECK	1 hour 30 minutes	
Health and Disease Overview: Diabetes type 1, Prematurity, Sickle cell disease, Asthma	1 hour	
Building Relationships and Motivational Interviewing: Trust, Communication, Coping and support, Respect and patient-centeredness	1 hour	
Self-Advocacy: Advocating for yourself, teaching patients to self-advocate	30 minutes	
Teamwork and Conflict Resolution: Teamwork, Conflict resolution	30 minutes	
Managing Transitions: Transitioning from adolescence to adulthood, Transitioning from pediatric to adult care, Hospital to home	30 minutes	

CHECK Basic CHW Training Program

Home Visitation: Why home visits, Preparing for a home visit, Safety, Home visit etiquette, Building trust, Mandatory reporting	1 hour
Self-Management: Problem solving, Social support, Environmental rearrangement, Self- monitoring, Action planning	1 hour
Operations: Office tour, Supplies (obtain laptop, office supplies, keys, office space, business cards, parking card), Building access, Job description, Job management (evaluations, monitoring, union, hours, scheduling, payroll, meetings, supervision)	3 hours
Teams and Protocols: Geographic zones/teams, Mobile van/dentistry, Phone protocols, Assessment protocols, Mental health specialists, disease specific teams (asthma, diabetes, sickle cell disease, prematurity), Hospital protocols, Tour	4 hours
Insurance: Medicaid managed care companies, Medical neighborhoods	1 hour
Community Outreach Basics of community outreach, Community-based medical neighborhood, Tour	1 hour 30 minutes
Medical Legal Issues: Medical legal team, Social Security, Education issues (504 plans and Individual Education Plans)	1 hour
Technology: Data access, use, and support; Purple binder; Compliance and HIPAA	2 hours

CHWs will be familiarized with the study protocol, clinic and WIC site policies, home visitation strategies, and documentation. CHWs will complete the 12-hour Mental Health First Aid course (*www.mentalhealthfirstaid.org*). [name] will then teach and practice basic motivational interviewing (4 hours). CHWs will shadow experienced CHWs on other projects at UIC for a minimum of three visits and they will shadow UIC dental clinicians for a minimum of 20 hours before being ready for field work. The first three CHW home visits will be conducted with the CHW supervisor. The CHW supervisor will score each visit using the CHW Fidelity Assessment Form (Appendix I). When the CHW scores at least 4 in each category on three visits, the CHW is ready to visit participants alone.

Phase 3: Ongoing Training

CHWs will receive continual education that includes monthly reviews of topics of interest to the CHWs, as well as participation in general CHW events conducted by the Chicago CHW Local Network (*http://chwnetwork.wordpress.com/*) and the CHECK Care Coordination team. Continual education includes oral health topics as needed (see Section 6.3.3.)

